#### 4.6 Justification for Dose

The MABEL approach was used to determine a safe first in human starting dose for FPT155. This approach was used because FPT155 functions through 2 key T cell regulators or modulators, including co-stimulation of CD28 on T cells after T cell receptor engagement, and blocking CTLA-4 from competing for endogenous CD80.

The FPT155 starting dose was based on the established guidelines for MABEL dosing and relevant literature ([Saber 2016](#)). Based on these guidelines, RO and PA between 20-80% are appropriate for selecting starting doses. For FPT155, assessments of RO and PA through both CTLA-4 and CD28 were considered. To project the human dose based on  $C_{max}$ , assumptions of a plasma volume of distribution of central compartment of 2800 mL and a 70 kg average patient weight were used in calculating the percent RO and PA.

Integrating the assessments of RO and PA through both CTLA-4 and CD28, a starting dose of 0.07 mg was selected. Among the PA assays examined, CTLA-4 ELISA was thought to be both biologically relevant and sensitive. Using this ELISA assay, 50% PA leads to a predicted starting dose, when rounded down, of 0.07 mg. Several PA assays for CD28 activity were considered, however these assays were either thought to be not biologically relevant or predicted a much higher starting dose.

The Sponsor has selected a Q3W dosing interval. Although the half-life of FPT155 in patients is predicted to be less than 10 days, preclinical evidence suggests that the total exposure, not  $C_{trough}$ , may be an important driver of efficacy. A Q3W interval between doses was thought to be appropriate because no target trough concentration has been identified to achieve between dose interval from nonclinical efficacy studies.

The Phase 1a dose escalation portion of the study will use an initial accelerated titration design followed by a standard 3+3 design, with patients enrolled across approximately 13 planned dose levels. The starting dose of 0.07 mg is predicted to attain a nominal (< 1%) PA for CD28 using the binding assay of Chinese hamster ovary (CHO) cells overexpressing CD28. The proposed dosing increments also take into consideration PA through both CD28 and CTLA-4. Fixed 3-fold escalation increments are proposed while PA of CD28 is low, with more conservative increments proposed at higher expected CD28 activity levels. Two fold or smaller increments in dose were used in dose escalation from 21mg to 560mg. During dose escalation, FPT155 is projected to achieve 99% PA for CTLA-4 at  $C_{max}$  for doses  $\geq 7$  mg. Based on the  $K_D$  and observed  $C_{max}$ , ipilimumab, an anti-CTLA4 antibody, was projected to achieve 99% RO for CTLA-4 at the clinically approved dose of 3 mg/kg ([BMS 2011](#), [He 2017](#), [Yervoy 2018](#)).

Preliminary pharmacokinetic results are consistent with dose-proportional increases in exposure with an absence of dose-limiting toxicities through the 560 mg dose level. As immune-related adverse events have been manageable in accordance with consensus guidelines and no MTD has been identified, dose escalation above 560mg uses 1.5-fold increments. The dose escalation cohorts are summarized below ([Table 8](#)).

**Table 8: FPT155 Phase 1 Dose Escalation Cohorts**

Cohort	Dose Level (mg)
1aM1	0.07
1aM2	0.21
1aM3	0.7
1aM4	2.1
1aM5	7
1aM6	21
1aM7	42
1aM8	70
1aM9	140
1aM10	280
1aM11	560
1aM12	840
1aM13	1260

Given many practical advantages, such as decreased operational difficulty, decreased compound waste, and reduced dosing errors, flat dosing will be used for this Phase 1 trial. PK variability introduced by either body weight-based or fixed dosing regimens is moderate relative to the variability generally observed in PD, efficacy, and safety ([Bai 2012](#)). Therefore, testing either body weight-based or fixed dosing regimens in phase 1 can achieve the goal of characterizing

PK. Assessment of the effect of body weight on PK will be conducted to determine the appropriate dosing approach and to support the proposed dose and dose regimen(s) for future trials using PK data collected from Phase 1.

Preclinical results show the potential for synergistic benefit from the combination of FPT155 and pembrolizumab. Pembrolizumab will be administered at the approved dose and schedule – 200mg IV Q3W. To mitigate the risk of increased immune-related toxicity, FPT155 dose escalation in combination with pembrolizumab will start at least two dose levels below the highest cleared FPT155 monotherapy dose level reflecting a four-fold reduction in FPT155 dose. Preclinical animal models demonstrated a reduction in the activity of the FPT155 and pembrolizumab combination with a three-fold reduction in FPT155 dose.

Approved

## 5.0 STUDY POPULATION

Prospective approval of protocol deviations to recruitment and enrollment criteria, also known as protocol waivers or exemptions, is not permitted.

### 5.1 Inclusion Criteria

Patients are eligible to be included in the study only if all of the following criteria apply:

#### Age

- 1.01) Patient must be 18 years of age or older at the time of signing the informed consent.

#### Type of Patient and Disease Characteristics

- 2.01) Histologically confirmed solid tumors (except primary CNS tumors). For patients enrolled for treatment with FPT155+pembrolizumab: histologically confirmed non-small cell lung cancer not eligible for curative therapy.
- 2.02) For patients in Phase 1a dose escalation (all) and Phase 1a dose exploration (FPT155 monotherapy) only: Disease that is unresectable, locally advanced, or metastatic and has progressed following all standard treatments or is not appropriate for standard treatments.
- 2.03) All patients must have at least one measurable lesion at baseline according to RECIST v1.1. Tumor sites situated in a previously irradiated area, or in an area subjected to other loco-regional therapy, are not considered measurable unless there has been demonstrated progression in the lesion.
- 2.04) Availability of archival tumor tissue and consent to provide archival tumor for retrospective biomarker analysis, or consent to undergo a fresh tumor biopsy during screening
- 2.05) For patients participating in Phase 1a dose exploration cohorts and Phase 1b dose expansion: consent to undergo a mandatory fresh tumor biopsy during screening and on treatment
- 2.06) ECOG performance status of 0 or 1
- 2.07) Life expectancy of at least 3 months in the opinion of the investigator
- 2.08) Willing and able to comply with all study procedures
- 2.09) Prior radiotherapy must be completed at least 2 weeks before first dose of study treatment administration. No radiopharmaceuticals (eg, strontium, samarium) within 8 weeks before first dose of study treatment administration
- 2.10) Prior surgery that requires general anesthesia must be completed at least 14 days before first dose of study treatment administration unless patients have recovered, and it is considered safe after discussion with medical monitor. Surgery requiring local/epidural

anesthesia must be completed at least 72 hours before first dose of study treatment administration and patients must have recovered.

2.11) Screening laboratory values must meet the following criteria:

**Hematologic**

- a. Neutrophils  $\geq 1.2 \times 10^9/L$
- b. Platelets  $\geq 75 \times 10^9/L$
- c. Hemoglobin  $\geq 9.0 \text{ g/dL}$
- d. Serum creatinine  $< 1.5 \times \text{ULN}$  or creatinine clearance of  $\geq 40 \text{ mL/minute}$  (using Cockcroft/Gault Formula)

$$\text{Female creatinine clearance (CrCl)} = \frac{(140 - \text{age in years}) \times (\text{weight in kg}) \times 0.85}{72 \times (\text{serum creatinine in mg/dL})}$$

$$\text{Male CrCl} = \frac{(140 - \text{age in years}) \times (\text{weight in kg})}{72 \times (\text{serum creatinine in mg/dL})}$$

- e. Prothrombin time (PT)/International normalized ratio (INR)  $< 1.5 \times \text{ULN}$  and partial thromboplastin time (PTT) (activated partial thromboplastin time [aPTT])  $< 1.5 \times \text{ULN}$  except for patients receiving anticoagulation, who must be on a stable dose of warfarin for 6 weeks prior to enrollment

**Hepatic**

- f. AST or ALT  $< 3 \times \text{ULN}$
- g. Bilirubin  $< 1.5 \times \text{ULN}$  (except patients with Gilbert's syndrome, who must have total bilirubin  $< 3 \text{ mg/dL}$ )
- h. Albumin  $\geq 3.0 \text{ g/dL}$  (patients with pancreatic cancer only)

**Sex**

3.01) Male or female

**General Inclusion Criteria**

**Reproductive Status**

Male patients:

4.01) A male patient must agree to use contraception as detailed in [Appendix 3](#) of this protocol during the treatment period and at least 2 months or 5 half-lives, whichever is longer, after the last dose of study treatment and refrain from donating sperm during this period.

Female patients:

5.01) A female patient is eligible to participate if she is not pregnant (see [Appendix 3](#)), not breastfeeding, and at least one of the following conditions applies:

- Not a woman of childbearing potential (WOCBP) as defined in [Appendix 3](#)

OR

- A WOCBP who agrees to follow the contraceptive guidance in [Appendix 3](#) during the treatment period and for at least 2 months or 5 half-lives, whichever is longer, after the last dose of study treatment.

## **Informed Consent**

6.01) Capable of giving signed informed consent as described in Section [10.3](#) which includes compliance with the requirements and restrictions listed in the informed consent form (ICF) and in this protocol

## **5.2 Additional Inclusion Criteria - Monotherapy (Phase 1b Only)**

### **Cohort 1b1: Renal Cell Carcinoma**

7.01) Patients with histologically or cytologically confirmed advanced or metastatic renal cell carcinoma with a clear-cell component.

7.02) Must have received at least one prior anti-angiogenic therapy regimen (eg, sunitinib, sorafenib, pazopanib, axitinib, tivozanib, or bevacizumab) in the advanced or metastatic setting

7.03) Must have received at least one anti-PD(L1) therapy (eg, nivolumab, pembrolizumab, atezolizumab, durvalumab, or avelumab) in the advanced or metastatic setting. Prior cytokine therapy (eg, IL-2, IFN- $\alpha$ ) and anti-CTLA-4 therapy (eg, ipilimumab) is allowed but not required.

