#### 4.1.3 Phase 1b FPT155 Monotherapy Dose Expansion

Enrollment in Phase 1b dose expansion will begin when the MTD and/or RD has been identified by the CRC. If additional cumulative safety or preliminary efficacy results from dose escalation or exploration suggest that an alternate dose or schedule may improve the benefit relative to risk in treatment with FPT155, more than one dose or schedule may be evaluated in the phase 1b cohorts.

Up to 8 tumor-specific cohorts consisting of approximately 30 patients each will evaluate the safety, efficacy, PK, and PD of FPT155 at a RD (see [Appendix 11](#)). Patients with advanced RCC and melanoma who have failed prior anti-PD(L)1 therapy will be enrolled in 2 of the 8 cohorts.

Additional tumor types for the remaining Phase 1b cohorts will be determined based on emerging safety, translational, and clinical data for FPT155, as well as any potential new safety signals from other immunotherapies, such as significant changes to prescribing information for approved immunotherapies.

Intensive monitoring will occur in the outpatient setting and include a minimum 6-hour observation window following completion of the first and second infusions. Additional monitoring requirements may be implemented based on emerging safety data from Phase 1a dose escalation.

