#### 4.5 Scientific Rationale for Study Design

The study is designed as an initial accelerated titration followed by a standard 3+3 dose escalation. The initial accelerated titration component may reduce the number of patients receiving potentially subtherapeutic doses of the study drug. The 3+3 design is chosen to avoid selection of a Phase 2 clinical trial dose that causes a treatment-limiting toxicity in more than 17% of patients, which is a standard that has been considered acceptable as an outpatient therapeutic for patients with limited options and life-threatening disease. This design has the advantage of being rule-based, allocates the lowest dose level to the first cohort, and adaptively escalates/de-escalates based on observed DLTs. Its execution is straightforward and generally well understood by clinicians and investigators, decreasing the potential for deviations from protocol.

Phase 1a dose exploration with mandatory pre- and on-treatment biopsies at doses  $\leq$  MTD will provide additional insight into the safety, PK, PD and mechanism of action of FPT155 and may help in determining the RD for Phase 1b.

Phase 1b for FPT155 monotherapy includes up to 8 tumor-specific cohorts. Patients with advanced RCC and melanoma that have failed prior anti-PD(L)1 therapy will be enrolled in 2 of the 8 cohorts. These patients have a poor prognosis and enrolling them will enable evaluation of the clinical activity of FPT155 in these typically immune-competent tumors that have progressed on a checkpoint inhibitor. Additional tumor types for the remaining 6 Phase 1b cohorts ([Appendix 11](#)) will be determined based on emerging safety, translational, and clinical data for FPT155, as well as any potential new safety signals from other immunotherapies, such as significant changes to prescribing information for approved immunotherapies.

Combination dose escalation with FPT155 and pembrolizumab will start with a FPT155 dose that is a minimum of two dose levels lower than the highest dose cleared during evaluation of FPT155 monotherapy as outlined below in [Table 8](#). Additional patients may be added in combination dose exploration at one or more dose levels that are cleared during combination dose escalation to better characterize the safety profile and preliminary clinical activity. The combination will be limited to patients with non-small cell lung cancer to maximize on the ability to interpret results from the limited enrollment that is planned.

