### **Cohort 1b2: Melanoma**

8.01) Patients with histologically- or cytologically-confirmed unresectable stage III or stage IV cutaneous melanoma not amenable to local therapy

8.02) Must have received at least one anti-PD(L1) therapy (including but not limited to nivolumab, pembrolizumab, atezolizumab, durvalumab, and avelumab) in the advanced or metastatic setting. Prior cytokine therapy (eg, IL-2, IFN- $\alpha$ ) and anti-CTLA-4 therapy (eg, ipilimumab) is also allowed.

8.03) Patients with BRAF mutations must have received prior BRAF inhibitor therapy (eg vemurafenib and dabrafenib) in the advanced or metastatic setting.

9.01) Inclusion Criteria for Additional Phase 1b Cohorts are included in [Appendix 11](#).

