2.2.3 FPT155 Monotherapy Dose Expansion

Enrollment in Phase 1b dose expansion will begin when the MTD and/or RD has been identified by the Cohort Review Committee (CRC). Up to 8 tumor-specific cohorts consisting of approximately 30 patients each will evaluate the safety, efficacy, PK, and PD of FPT155 at the RD. Patients with advanced renal cell carcinoma (RCC) and melanoma that have failed prior anti-programmed death-ligand 1 (anti-PD[L]1) therapy will be enrolled in 2 of the 8 cohorts. Additional tumor types are specified in [Table 3](#) for the remaining Phase 1b cohorts and will be determined based on emerging safety, translational, and clinical data for FPT155, as well as any potential new safety signals from other immunotherapies, such as significant changes to prescribing information for approved immunotherapies.

Table 3 Additional Cohorts for Phase 1b Expansion

Phase 1b Cohort	Inclusion Criteria
1	Patients with advanced renal cell carcinoma as specified per Section 5.2 of the protocol.
2	Patients with advanced melanoma as specified per Section 5.2 of the protocol.
3	Patients with previously-treated unresectable or metastatic solid tumors with deficient mismatch repair (dMMR) or high microsatellite instability (MSI-H) and an absence of suitable standard treatment options.
4	Patients with previously-treated unresectable or metastatic non-small cell lung cancer and an absence of suitable standard treatment options.
5	Patients with previously-treated solid tumors with a response to prior PD-1 or PDL-1 directed treatment as defined by an objective response (partial or complete response) or a minimum of three months on prior PD-1 or PDL-1 directed therapy.

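### The RCC and melanoma expansion criteria ask only that anti-PD(L)1 therapy was received, while the design text and the SAP describe patients who failed or progressed on it, so the cohort ORR need not describe the stated population

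*Protocol*

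**What the plan says.** **Stated population.** Protocol Section 4.1.3 says: "Patients with advanced RCC and melanoma who have failed prior anti-PD(L)1 therapy will be enrolled in 2 of the 8 cohorts". Section 4.5 gives the reason for choosing them: the aim is to evaluate clinical activity in "these typically immune-competent tumors that have progressed on a checkpoint inhibitor". The synopsis paragraph on monotherapy dose expansion also describes these patients as having failed such therapy. SAP Section 2.2.3 agrees: patients "that have failed prior anti-programmed death-ligand 1 (anti-PD[L]1) therapy will be enrolled in 2 of the 8 cohorts".

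**Entry criteria.** Protocol Section 5.2, criterion 7.03 (RCC), reads "Must have received at least one anti-PD(L1) therapy (eg, nivolumab, pembrolizumab, atezolizumab, durvalumab, or avelumab) in the advanced or metastatic setting". Criterion 8.02 (melanoma) begins "Must have received at least one anti-PD(L1) therapy (including but not limited to" and then lists agents in the same way. The synopsis repeats both. Neither mentions failure or progression.

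**Sizing.** Protocol Section 9.2 and SAP Section 2.3 plan up to 30 patients per cohort to give 25 evaluable, so that an observed ORR of 24% or more excludes 10%. Table 10 of the protocol (Table 4 of the SAP) gives a 90% interval of 11% to 42% for 6/25.

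**The concern.** The two cohorts are in the design because activity after progression on a checkpoint inhibitor would be informative. If entry depends only on exposure, a site that follows Section 5 can enrol a patient who completed or chose to stop anti-PD(L)1 therapy in stable disease or partial response and still has measurable tumour.

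Such a patient may still be sensitive to checkpoint inhibition. A response would be counted in an ORR that the protocol text presents as coming from patients whose prior anti-PD(L)1 therapy had failed. With no control arm, a reader of the cohort result would have no sign that the denominator mixes two kinds of patient. What is at stake is the meaning of the ORR in two of the five Phase 1b cohorts listed in Appendix 11.

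**Working it through.** **Step 1. Does another criterion supply the missing condition?**

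| Provision | What it does | Closes the gap? |
|---|---|---|
| Inclusion 2.02 (progressed after all standard treatments) | Opens with "For patients in Phase 1a dose escalation (all) and Phase 1a dose exploration (FPT155 monotherapy) only" | No, Phase 1b is outside it |
| Inclusion 2.03 (measurable disease) | Asks for progression only in lesions previously irradiated or locally treated | No |
| Exclusion 2.03 | Excludes patients who stopped prior immunotherapy for toxicity; requires 5 half-lives or 90 days since the last dose, whichever is shorter | Narrows it only |
| Inclusion 7.02 (RCC) | Requires prior anti-angiogenic therapy | No |
| Inclusion 8.03 (melanoma) | Requires prior BRAF inhibitor if BRAF-mutated | No |
| Appendix 11, cohorts 1 and 2 | Refers back to Section 5.2 | No |
| Appendix 11, cohorts 3 and 4 | Adds lack of suitable standard options | Does not apply to cohorts 1 and 2 |

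Section 8.2 makes the Section 5 criteria the test for enrolment.

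**Step 2. Does the analysis correct it?** The response-evaluable population (SAP Section 4.5) requires that eligibility was met, and these patients meet it. SAP Sections 6.1.4.2 and 6.1.7 summarise best response to the last regimen. That regimen need not be the anti-PD(L)1 one, and a best response does not show later progression. No ORR analysis by progression status appears in the readable SAP text.

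**Step 3. Reproduce the plan's figure.** The Clopper-Pearson 90% limits for x/n are the 5% quantile of Beta(x, n−x+1) and the 95% quantile of Beta(x+1, n−x). For 6/25 they are 11.0% and 42.0%, as in Table 10. For 5/25 the lower limit is 8.2%, so 6 is the smallest count that excludes 10%.

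**Step 4. Illustrate the effect.** Call patients who progressed on anti-PD(L)1 refractory, with response probability p. Let k of the 25 be other patients, with response probability r. Responses are the sum of Binomial(25−k, p) and Binomial(k, r), and the expected ORR is [(25−k)p + kr]/25. The values of k, p and r are all assumed.

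The upper part of the r range borrows the ORRs that protocol Section 2.1 cites for anti-PD-1 agents: 25% in RCC after anti-angiogenic therapy, and 33–40% in melanoma. Those are results for other drugs. The 15% value is a lower case added for balance.

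| p | k | r | Expected ORR | P(at least 6/25) |
|---|---|---|---|---|
| 10% | 0 | – | 10.0% | 3.3% |
| 10% | 5 | 15% | (2.0+0.75)/25 = 11.0% | 5.0% |
| 10% | 5 | 25% | (2.0+1.25)/25 = 13.0% | 9.3% |
| 10% | 5 | 40% | (2.0+2.0)/25 = 16.0% | 18.8% |
| 5% | 0 | – | 5.0% | 0.1% |
| 5% | 5 | 15% | (1.0+0.75)/25 = 7.0% | 0.6% |
| 5% | 5 | 25% | (1.0+1.25)/25 = 9.0% | 1.6% |
| 5% | 5 | 40% | (1.0+2.0)/25 = 12.0% | 5.0% |

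At p = 10%, 3 such patients with r of 25% to 40% give 6.4% to 10.5%, and 8 give 15.0% to 35.9%.

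**Step 5. Check on the primary efficacy denominator.** The primary efficacy analysis uses all treated patients, about 30 per cohort. There the smallest count that excludes 10% is 7/30 (lower limit 11.5%). At p = 10% its probability is 2.6% with no such patients, and 8.2% to 18.1% with 6 of 30 at r of 25% to 40%. The picture is the same.

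**The case against.** The mismatch in wording cannot be disputed, but several stronger readings go beyond the documents.

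- **That the false-positive rate is inflated.** A reader might infer this from the probabilities above. Phase 1b's primary endpoint is safety, ORR is secondary, the protocol states no hypothesis, and all analyses are descriptive. No go/no-go rule is attached to 6/25; the 24% figure is a statement about interval width. This objection stands in full.
- **That 10% is a benchmark for refractory disease.** Section 9.2 applies it to every cohort. That includes cohort 5, which selects patients who responded to PD-1 or PD-L1 therapy or spent at least three months on it. This also stands.
- **That inflation is established.** It requires the other patients to respond to FPT155 more often than refractory ones, and nothing in the documents shows that. The only clinical response data, in Section 2.3, are one unconfirmed partial response and otherwise stable disease at best. The direction is plausible but conditional.
- **That the groups can never be separated.** Prior anticancer therapy is collected and listed by subject, so much could be recovered. What is missing is a planned record of progression on the anti-PD(L)1 regimen and an analysis that uses it.
- **That the entry route is wide.** Patients who stopped for toxicity are excluded. Continued shrinkage from the earlier drug would have to amount to a partial response against a new baseline scan and be confirmed at least 4 weeks later.

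It can also be argued that Section 10.1.3 requires the whole protocol to be followed, Section 4.1.3 included. That leaves a site with two conflicting statements and does not supply a criterion.

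**Conclusion.** The inconsistency is real and should be fixed. As written, criteria 7.03 and 8.02 define patients exposed to anti-PD(L)1 therapy, whereas Sections 4.1.3 and 4.5, the synopsis and SAP Section 2.2.3 describe patients in whom it failed. An ORR from a cohort enrolled under the written criteria need not describe the stated population.

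The size is unknown. If 5 of 25 patients fall outside that population and respond with probability 15% to 40%, the expected ORR moves from 10% to between 11% and 16%, or from 5% to between 7% and 12%. The chance of at least 6/25 moves from 3.3% to between 5.0% and 18.8%, or from 0.1% to between 0.6% and 5.0%. The number of such patients and both response rates are assumptions. If sites enrol only patients who progressed, or if response does not differ by progression status, there is no bias.

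The consequence is a misread estimate, not a breach of type I error, because the plan makes no test or decision that could be breached.

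**What to change.** Reconcile the passages. The preferred route is to add documented disease progression on anti-PD(L)1 therapy to criteria 7.03 and 8.02 and to their copies in the synopsis. The criteria would then match Sections 4.1.3 and 4.5 and SAP Section 2.2.3. State explicitly whether progression after stopping also qualifies: Section 4.5 speaks of progression on the drug, and a patient who responded, stopped and relapsed later may still be checkpoint-sensitive.

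If the broader population is intended, describe the cohorts as anti-PD(L)1-experienced in those sections and in the SAP. In that case, and for any patients already enrolled, record progression status on the prior anti-PD(L)1 regimen and report ORR by that status.

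The cost is one clause in two criteria and slightly narrower eligibility. The alternative costs one data item and one additional ORR table, with small subgroups that can only be described.
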